5.2.2 Clinical Global Impression–Improvement (CGI-I)

The CGI-I scale is used by the clinician to rate how much the subject's illness has improved or worsened relative to a baseline state. A 7-point scale is used from 1=very much improved, 2=much improved, 3=minimally improved, 4=no change, 5=minimally worse, 6=much worse, 7=very much worse.

Higher CGI-I scores denote more severe illness and less improvement in the illness respectively.

5.2.3 Communication and Symbolic Behavior Scales Developmental Profile™ Infant-Toddler Checklist – Social Composite Score (CSBS-DP-IT Social)

The Checklist consists of 24 questions that range from 0 to 4 points within each of 7 Clusters. Credit of 0 points is given for items checked “Not Yet”, 1 point for items checked “Sometimes”, or 2 points for items checked “Often”. For items that describe a series of numbers or ranges, credit of 0 points is given for items checked “None” and 1 to 4 points for items containing numbered choices.

Three composite scores assessing 7 skill areas can be calculated. The Social Composite score is comprised of 13 items in the skill areas “Emotion and Eye Gaze” (items 1 to 4), “Communication” (items 5 to 8), and “Gestures” (items 9 to 13). The Speech Composite score, including the skill areas “Sounds” and “Words” is based on items 14 to 18. The Symbolic Composite score, including the skill areas “Understanding” and “Object Use”, is based on items 19 to 24.

The Social Composite raw score (comprised of items 1 to 13) ranging from 0 to 26 will be calculated as the sum of the scores for all 13 items. Higher Social Composite raw scores indicate better social communication development. If there are 2 or less missing item scores, the Social Composite raw score will be calculated by the arithmetic mean of the non-missing item scores multiplied by 13, rounded to the nearest integer. The Social Composite raw score will be considered as missing if there are missing scores for 3 or more items.

5.2.4 Overall Quality of Life Rating of the Impact of Childhood Neurologic Disability (ICND) Scale

The overall quality of life score rating of the ICND will be analyzed as a separate endpoint. The numeric scale of the child's overall quality of life ranges from 1 (“Poor”) to 6 (“Excellent”); lower overall quality of life scores indicate lower quality of life.

5.2.5 Rett Syndrome Clinician Rating of Hand Function (RTT-HF)

The RTT-HF is a clinician completed clinical assessment of the subject's ability to use her hands for functional purposes. The assessment is made on an 8-point Likert scale (0-7) with 0 denoting normal functioning and 7 the most severe impairment.

5.2.6 Rett Syndrome Clinician Rating of Ambulation and Gross Motor Skills (RTT-AMB)

The RTT-AMB is a clinician completed clinical assessment of the subject's ability to sit, stand, and ambulate. The assessment is made on an 8-point Likert scale (0-7) with 0 denoting normal functioning and 7 the most severe impairment.

5.2.7 Rett Syndrome Clinician Rating of Ability to Communicate Choices (RTT-COMC)

The RTT-COMC is a clinician completed clinical assessment of the subject's ability to communicate her choices or preferences, which can include the use of nonverbal means such as eye contact or gestures. The assessment is made on an 8-point Likert scale (0-7) with 0 denoting normal functioning and 7 the most severe impairment.

5.2.8 Rett Syndrome Clinician Rating of Verbal Communication (RTT-VCOM)

The RTT-VCOM is a clinician completed clinical assessment of the subject's ability to communicate verbally. The assessment is made on an 8-point Likert scale (0-7) with 0 denoting normal functioning and 7 the most severe impairment.

5.2.9 Clinical Global Impression–Severity (CGI-S)

The CGI-S is a 7-point scale that requires the clinician to rate the severity of the subject's illness at the time of assessment, relative to the clinician's experience with subjects who have the same diagnosis. Considering total clinical experience, a subject is assessed on severity of illness at the time of rating: 1=normal, not at all ill; 2=borderline ill; 3=mildly ill; 4= moderately ill; 5=markedly ill; 6=severely ill; or 7=extremely ill.

Higher CGI-S scores denote more severe illness and less improvement in the illness respectively.

5.2.10 Rett Syndrome Caregiver Burden Inventory (RTT-CBI)

The RTT-CBI consists of 24 negatively worded items (Items 1 through 24). Frequency ratings are on a 5-point Likert scale including: 0=never; 1=rarely; 2=sometimes; 3=frequently and 4=nearly always. The RTT-CBI also includes 2 positively worded items (items 25 and 26) that comprise the Optimism Index; this index will not be used for analysis. The total score ranging from 0 to 96

will be calculated as the sum of the scores for Items 1-24. If there are 4 or fewer missing item scores, the RTT-CBI total score will be calculated by the arithmetic mean of the non-missing item scores multiplied by 24, rounded to the nearest integer. The RTT-CBI total score will be considered as missing if there are missing scores for 5 or more items.

5.2.11 Impact of Childhood Neurologic Disability (ICND) Scale Total Score

The ICND scale evaluates the effect of four health problems on 11 aspects of the child's or the family's life which are scored 0 ("Not at all"), 1 ("A little"), 2 ("Some"), 3 ("A lot"), or "Does not apply". The four health problems are 1) inattentiveness, impulsivity, or mood, 2) ability to think and remember, 3) neurologic or physical limitations, and 4) epilepsy. The ICND total score ranging from 0 to 132 will be calculated as follows:

1. For each health problem, the score will be calculated as the sum of the 11 item scores. The health problem score will be considered missing
 - a. if more than 5 item scores are either missing or "Does not apply"
 - b. or if more than 3 item scores are missing for reasons other than the response of "Does not apply".
2. The ICND total score will be calculated as the sum of the average of each problem score multiplied by 11.

$$ICND \text{ Total Score} = \sum_{k=1}^4 problem_score_average_k * 11$$

where k indexes the four health problems.

The ICND total score will be considered missing if at least 1 health problem score is missing. Imputed ICND total scores will be rounded to the nearest integer.

Higher ICND total scores indicate worse health problems. The ICND total score does not include the Overall Quality of Life Rating.

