2.2.1 Secondary Endpoints

The secondary endpoints for this study are:

- Rett Syndrome Behaviour Questionnaire (RSBQ) total score – Change from Baseline to Week 40
- Clinical Global Impression–Improvement (CGI-I) Score at Week 40 (assessing improvement from Baseline of the present study)

Change from Baseline to Week 40 in:

- Communication and Symbolic Behavior Scales-Developmental Profile™ Infant-Toddler Checklist – Social Composite Score (CSBS-DP-IT Social)
- Overall Quality of Life Rating of the Impact of Childhood Neurologic Disability (ICND) Scale
- Rett Syndrome Clinician Rating of Hand Function (RTT-HF)
- Rett Syndrome Clinician Rating of Ambulation and Gross Motor Skills (RTT-AMB)
- Rett Syndrome Clinician Rating of Ability to Communicate Choices (RTT-COMC)
- Rett Syndrome Clinician Rating of Verbal Communication (RTT-VCOM)
- Clinical Global Impression–Severity (CGI-S)
- Rett Syndrome Caregiver Burden Inventory (RTT-CBI) Total Score (items 1-24)
- Impact of Childhood Neurologic Disability (ICND) Scale Total Score

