9.5.3 Secondary Analyses

Descriptive summary statistics for RSBQ, CGI-I (observed value only, no change from Baseline), CGI-S, CSBS-DP-IT Social, ICND (QoL score and total score), each of the four Rett Syndrome Clinician Rating scales, and the RTT-CBI observed values and change from Baseline will be summarized by timepoint. For the CGI-I there will be descriptive summary statistics of the observed value only.

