5.1 General Data Reporting Conventions

Continuous variables will be summarized using the following descriptive statistics: number of subjects, mean, standard error (SE), standard deviation (SD), median, minimum, and maximum. For descriptive summaries of efficacy, the 95% confidence interval (CI), calculated as $\text{mean} \pm 1.96 * \text{SE}$, will be presented. Unless specified otherwise, means, medians, and CIs will be presented to one more decimal place than the raw data, and the SDs and SEs will be presented to two more decimal places than the raw data. In general, the maximum number of decimal places is 4 and values will be truncated to 4 decimal places in situations where there are more than 4 decimal places. Wherever possible data will be decimal aligned.

Height, weight and BMI will be presented with a maximum of one decimal place.

Categorical variables will be summarized by the number of subjects and the percentage of subjects in each category; the number of subjects and the percentage of subjects with missing data will be summarized for demographic and baseline characteristics (if applicable). Categories with zero counts will not have zero percentages displayed. For demographic summaries, percentages will be calculated by using the total number of subjects in the given treatment group of the antecedent study as the denominator. Percentages will be presented with one decimal place.

Duration in months will be calculated as ([the number of days / 365.25] *12).

Lab values, not including PK concentration data, that are collected with “<” or “>” signs will generally be analyzed as the numerical value without the sign in tables and figures. In listings, these data will be reported as collected with the sign.

For each continuous measure in safety and efficacy analyses, change from baseline results will be presented by treatment group of the antecedent study and overall in two ways:

1. Main analysis: using the baseline of this study, as defined in [Section 5.5](#), to report the changes across the timepoints of this open-label Study ACP-2566-004.
2. Exploratory analysis: using the baseline from the antecedent study, ACP-2566-003, to report the changes across the timepoints of this open-label Study ACP-2566-004.

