5.4 Baseline Definition

Data from the latest predose value of (Study ACP-2566-003 Week 12/EOT visit, unscheduled visit within Week 12 window, visit within 2 weeks of last double-blind dose, or Study ACP-2566-004 Baseline Visit) will be carried over as Baseline information in the present study, as applicable (e.g., not for the CGI-I for which this is not applicable).

Subjects for whom the Baseline visit of this study is not on the same day as the Week 12/EOT visit of the antecedent study (e.g., subjects in the antecedent study who were prevented from entering this study by the COVID-19 public health emergency) will have blood drawn for Baseline values three to fourteen days before the Baseline visit.

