13. METHODS OF EFFICACY ANALYSES

13.1 Analysis of Continuous Efficacy Endpoints

Descriptive statistics for all efficacy endpoints listed in [Section 12.1](#) will be tabulated by treatment group of the antecedent study. The summaries of the change from baseline results will be presented in two ways (main analysis and exploratory analysis) as specified in [Section 5.1](#).

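### Six or more "Does not apply" answers on one health problem void the whole ICND total, so entry into this secondary summary can depend on epilepsy status and on the caregiver's choice of answer

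*SAP*

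**What the plan says.** Change from Baseline to Week 40 in the "Impact of Childhood Neurologic Disability (ICND) Scale Total Score" is a secondary endpoint (Protocol 2.2.1). The caregiver judges four health problems, the fourth being epilepsy, on 11 aspects of daily life each. Answers score from 0 (*Not at all*) to 3 (*A lot*). *Does not apply* is also offered and carries no number (Protocol 6.1.4, SAP 5.2.11).

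SAP 5.2.11 has three rules for missing scores:

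- **Rule 1a:** a problem score is missing "if more than 5 item scores are either missing or" *Does not apply*, that is, from 6 of 11 upwards.
- **Rule 1b:** it is also missing if more than 3 items are "missing for reasons other than the response of" *Does not apply*.
- **Total:** "The ICND total score will be considered missing if at least 1 health problem score is missing".

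Otherwise the total sums, over the four problems, the mean item score times 11, with a stated range of 0 to 132. SAP 12.3 refers back to Section 5.2 and adds nothing.

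The scale is scheduled at Baseline and Visit 5 only. Values from the antecedent study "will be carried over as Baseline information in the present study, as applicable" (SAP 5.4). SAP 13.1 states that "The summaries of the change from baseline results will be presented in two ways". The main one uses this study's Baseline. The exploratory one is described in SAP 5.1 as "using the baseline from the antecedent study, ACP-2566-003, to report the changes across the timepoints of this open-label Study ACP-2566-004".

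Epilepsy is not assumed in every subject. Protocol 1.1 treats seizures as frequent but not diagnostic, and Protocol 6.3 has the seizure profile reviewed only where there is one.

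**The concern.** For a child without epilepsy, *Does not apply* is a natural answer to the epilepsy items. Under rule 1a it removes the total, whatever is recorded for the other three problems. Another caregiver of a similar child may mark *Not at all*, score 0 and stay in. Neither document says which answer to choose.

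So a stated rule, and not only dropout or skipped items, can select who is summarised. If it does, the ICND total describes a group tilted towards subjects with epilepsy. A caregiver who switches between the two answers from one visit to the next also changes who has a change score. With only two scheduled assessments in this study, there is little to fall back on.

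**Working it through.** **Inputs.** From SAP 5.2.11: 4 problems, 11 items each, scores 0 to 3, rules 1a and 1b, the total rule and the averaging formula. From SAP 3.5: up to about 180 subjects. The documents give neither the share of subjects without epilepsy nor how often *Does not apply* is chosen.

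**Plan's own figure.** Maximum 4 × 11 × 3 = 132, minimum 0. The stated range is reproduced.

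**Threshold.** Take a subject with *Some* (2 points) on every item of the other three problems: 3 × 11 × 2 = 66.

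| Epilepsy items | ICND total |
|---|---|
| 11 *Not at all* | 66 + 0 = 66 |
| 1–5 *Does not apply*, rest *Not at all* | 66 |
| 6–11 *Does not apply* | missing |

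**Clustering.** Six *Does not apply* answers in one problem are 6/44 = 13.6% of items. They void the total although 38 of 44 items are scored. If all 11 epilepsy items are *Does not apply*, 33 of 44 (75%) are scored and the total is void. Twenty such answers spread 5 per problem are 20/44 = 45.5%, and the total is valid.

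**Change scores.** Let A be the antecedent baseline, B this study's Baseline and W Week 40. The main change needs B and W; the exploratory change needs A and W. There are 7 possible patterns of void totals:

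- B only: the main change is lost.
- A only: the exploratory change is lost.
- W, AB, AW, BW or ABW: both are lost (5 of 7).

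A total valid at one visit still enters the observed-value summary for that visit.

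**Scaling (assumed losses).** With a share f of totals lost and equal SD, the standard error is multiplied by √(1/(1 − f)).

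- f = 10%: 180 × 0.10 = 18 lost; √(180/162) = 1.054.
- f = 40%: 180 × 0.40 = 72 lost; √(180/108) = 1.291.

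The factors do not depend on 180. The counts do, and they are upper limits because they ignore discontinuation.

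**Composition (constructed example).** Suppose subjects with epilepsy total 88 (*Some* throughout, 66 + 22) and those without total 66 if marked *Not at all*. With an assumed 30% without epilepsy, the observed mean is (126 × 88 + 54 × 66)/180 = 81.4 if all are kept, and 88.0 if all 54 are voided. With 10% without epilepsy the two means are 85.8 and 88.0; with 50% they are 77.0 and 88.0. This shows how the answer choice can act on observed values. It estimates nothing for this trial.

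**Remedy check.** The three-problem maximum is 3 × 11 × 3 = 99. That total is unaffected by any number of *Does not apply* answers on epilepsy. It is still void if another problem has 6 or more.

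**The case against.** The rule is coherent. It asks for a majority of scored items in each domain, and a four-domain total arguably needs all four domains. The contrast of 13.6% void with 45.5% valid is what any per-domain rule produces. This stands, and it is why the planned derivation should remain the main analysis.

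The loss would not be invisible. SAP 5.1 reports the number of subjects for each continuous variable. The ICND quality-of-life rating comes from the same assessment and is summarised separately, so comparing the two n's roughly shows how many totals are lost. Raw and derived scores are listed (SAP 5.2). This also stands. The comparison does not, however, separate *Does not apply* from blank items, or one health problem from another. The table specifications are a separate document and might add that breakdown.

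The loss may be zero. Caregivers receive standardised training (Protocol 6.1), and that training, the eCRF or the instrument's own instructions could direct them to *Not at all*. None of these is available here.

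A table limited to Baseline and Week 40 would be incomplete. The last ICND visit is 40/EOT/ET, early-termination assessments are windowed by study day (SAP 5.5, 5.5.1), and SAP 12.1 lists ICND change at Weeks 2, 12, 26 and 40. The fix below allows for this.

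A reader might infer that every subject without epilepsy is excluded, or that *Does not apply* ought to score 0. The documents support neither. Such a subject keeps the total under *Not at all*, and neither document says that the two answers mean the same.

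**Conclusion.** The point holds as a cheap improvement. Six or more *Does not apply* answers on one problem, with or without blank items among them, remove the whole total. Because epilepsy is one of the four problems and not every subject is assumed to have it, inclusion can depend on epilepsy status and on answer choice.

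The number affected cannot be derived and may be zero. The factors of 1.054 (10% lost) and 1.291 (40% lost) are scaling under assumed losses and equal SD. It would go too far to call the ICND summary biased: that requires the loss to occur, and no figure in the documents shows that it does.

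The reach is one descriptive secondary endpoint. Safety is primary, no hypothesis is tested, and the quality-of-life rating is unaffected.

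**What to change.** Keep the SAP 5.2.11 total as the main analysis, without re-scoring *Does not apply*. Add to SAP 5.2.11 and 13.1:

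1. A clearly labelled supplementary ICND total over the three problems other than epilepsy (range 0–99). Use the same rules 1a and 1b, and summarise it as observed value and change from Baseline.
2. A count of ICND totals voided under rule 1a by *Does not apply*, by health problem, at Baseline and at every post-Baseline analysis visit with ICND data, including windowed early-termination assessments. Counting a problem when rule 1a is met and rule 1b is not ensures that blank items alone are not the cause.

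The first stays computable when epilepsy does not apply and needs no view on what that answer means. The second shows whether anything was lost and for which problem.

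The cost is a few sentences and two summaries from items already collected. Baseline values of the three-problem total need item-level ICND data from the antecedent study. If that study's own baseline items are not available, the supplement is limited to change from this study's Baseline. The supplementary score omits any impact of epilepsy and cannot be compared with the 0–132 total. If caregivers were trained to mark *Not at all*, the count will simply show that no total was lost this way.

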5.3 Study Day

If the date of assessment occurs on or after the first dose date, then study day will be calculated as (date of assessment – date of first dose) + 1. If the date of assessment occurs prior to the first dose date, then study day will be calculated as (date of assessment – date of first dose). There is no study day 0.

5.4 Baseline Definition

Data from the latest predose value of (Study ACP-2566-003 Week 12/EOT visit, unscheduled visit within Week 12 window, visit within 2 weeks of last double-blind dose, or Study ACP-2566-004 Baseline Visit) will be carried over as Baseline information in the present study, as applicable (e.g., not for the CGI-I for which this is not applicable).

Subjects for whom the Baseline visit of this study is not on the same day as the Week 12/EOT visit of the antecedent study (e.g., subjects in the antecedent study who were prevented from entering this study by the COVID-19 public health emergency) will have blood drawn for Baseline values three to fourteen days before the Baseline visit.

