4.1 Inclusion Criteria

A subject must meet all of the following inclusion criteria to be eligible for participation in the study:

1. Informed consent prior to the conduct of any study procedures is required as follows:
 - a. For subjects who are minors: written informed consent will be obtained from the legally acceptable representative (LAR). The subject should provide written or oral assent if deemed able by the Investigator. The process of obtaining informed consent will be conducted in accordance with institutional review board (IRB) or ethics committee (EC) policy and applicable local law.

- b. For subjects who are not minors: written informed consent will be obtained from the LAR or the subject if deemed able by the Investigator. If the subject is deemed not able to provide consent, the subject should provide written or oral assent if deemed able by the Investigator. The process of obtaining informed consent will be conducted in accordance with IRB or EC policy and applicable local law.
 - c. The subject's caregiver must also provide written informed consent regarding their participation in the study prior to participating in any study procedures.
2. Has completed the Week 12/EOT visit of the antecedent study, Study ACP-2566-003
NOTE: An exception is made for subjects who either discontinued from or completed but did not directly rollover from the antecedent study due to the COVID-19 public health emergency. These subjects may enroll in this study within 12 months of their withdrawal/completion from the antecedent study, with approval of the Sponsor or Medical Monitor.
3. Met all entry criteria for the antecedent study
4. May benefit from long-term treatment with open-label trofinetide in the judgment of the Investigator
5. Can still swallow the study medication provided as a liquid solution or can take it by gastrostomy tube
6. The subject's caregiver is English-speaking and has sufficient language skills to complete the caregiver assessments

Childbearing Potential

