6.1.7 Rett Syndrome Clinician Rating of Ability to Communicate Choices (RTT-COMC)

The Rett Syndrome Clinician Rating of Ability to Communicate Choices is a clinician completed clinical assessment of the subject's ability to communicate her choices or preferences, which can include the use of nonverbal means such as eye contact or gestures. The assessment is made on an 8-point Likert scale (0-7) with 0 denoting normal functioning and 7 the most severe impairment. This rating is a further development of the RTT-DSC Language/Communication Rating used in Study Neu-2566-RETT-002.

The assessment will be administered at Baseline and at all other designated visits when the visit takes place in the clinic. When a study visit takes place off-site, the RTT-COMC should be completed if possible, but it is not required.

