6.2.5 Laboratory Evaluations

Laboratory evaluations will be completed according to the schedule presented in [Table S-2](#) and procedures detailed in the laboratory manual. Additional safety testing may be performed at the discretion of the Investigator or designee.

Clinical laboratory sample collection is not required to be completed under fasting conditions. The laboratory evaluations will include the following:

- Clinical chemistry serum tests

- Sodium (Na), potassium (K), chloride (Cl), phosphorus (P), calcium (Ca), carbon dioxide (CO₂), blood urea nitrogen (BUN), creatinine (CR), uric acid
- Alanine aminotransferase (ALT), aspartate aminotransferase (AST), gamma-glutamyl transpeptidase (GGT), alkaline phosphatase (ALP), total bilirubin (TBIL), lactate dehydrogenase (LDH)
- Glucose
- Albumin (ALB), total protein
- Thyroid stimulating hormone (TSH), free T3, and free T4
 - Thyroid function tests will be performed at Visit 1 (Baseline) and Visit 5
- Pregnancy test
 - A serum pregnancy test will be performed at all designated visits ([Table S-2](#)) for subjects of childbearing potential
- Hematology tests
 - Complete blood count (CBC) including:
 - White blood cell (WBC) count
 - Complete differential (relative and absolute)
 - Hematocrit (Hct), hemoglobin, red blood cells (RBC), platelets
 - Reticulocyte count
- Urinalysis
 - Blood, RBCs, WBCs, protein, glucose, ketones, specific gravity, pH
 - Reasonable efforts will be made to collect a urine sample from all subjects. When collection of a urine sample proves impractical or impossible (e.g., because the subject is incontinent or unable to cooperate), failure to collect a urine sample will be recorded in the subject's eCRF, and will not be considered a protocol deviation

Subjects for whom the Baseline visit of this study is not on the same day as the Week 12/EOT visit of the antecedent study (e.g., subjects in the antecedent study who were prevented from entering this study by the COVID-19 public health emergency) will have blood drawn for Baseline values three to fourteen days before the Baseline visit. The investigator should have the results of the following standard laboratory studies available for review before enrolling the subject: the basic metabolic panel (Na, K, Cl, P, Ca, CO₂, BUN, and CR), serum glucose,

the liver function tests (ALT, AST, GGT, ALP, TBIL and LDH), serum pregnancy test (if the subject is of childbearing potential), and CBC.

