9.5 Statistical Analyses

9.5.1 General Approach

All endpoints will be summarized for the Safety Analysis Set. Additional summaries by prior treatment may be included.

Data from the Week 12/EOT visit procedures of Study ACP-2566-003 will be carried over as Baseline information in the present study, as applicable (e.g., not for the CGI-I). An exception is made for those subjects for whom it was not possible to use the Week 12/EOT visit of the antecedent study (ACP-2566-003) as the Baseline visit (Visit 1) because of the COVID-19 public health emergency. For those subjects, data from the Week 12/EOT visit procedures of Study ACP-2566-003 will not be carried over as Baseline information in the present study.

Continuous measurement results will be reported using the number of subjects with data values, mean, standard error of the mean, median, standard deviation, minimum, and maximum. For each categorical outcome, the frequency and percentage of subjects in each category will be reported.

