5.5 Analysis Visit Windows

Efficacy, safety, and PK assessments will be summarized by analysis visit as presented in Table 2 below.

Table 2 Analysis Visit Windows

| Analysis Visit | Target Study Day | Study Day Interval |
|------------------------|------------------|--------------------|
| Baseline (Day 1) | 1 | ≤ 1 |
| Day 1 Post First Dose* | 1 | 1 |
| Week 2 | 15 | 2 – 49 |
| Week 12 | 85 | 50 – 133 |
| Week 26 | 183 | 134 – 231 |
| Week 40 | 281 | 232 – 310 |

*For ECG and PK assessments only; other assessments post-first dose on Day 1 will go to the Week 2 analysis visit window.

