19. CHANGES TO ANALYSES SPECIFIED IN PROTOCOL

No changes are made to the analyses specified in the protocol.

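### SAP 5.4 leaves study 003 values eligible as Baseline for subjects with a COVID-19 gap, which protocol 9.5.1 rules out, while SAP 19 declares no change (small effect, wording fix)

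*SAP*

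**What the plan says.** Protocol 9.5.1 carries the Week 12/EOT data of the double-blind study ACP-2566-003 (003) into the present study (004) as Baseline, and then limits this: "An exception is made for those subjects for whom it was not possible to use the Week 12/EOT visit of the antecedent study" as Visit 1 because of COVID-19. For those subjects, "data from the Week 12/EOT visit procedures of Study ACP-2566-003 will not be carried over as Baseline information in the present study". The note to inclusion criterion 2 in protocol 4.1 sets the longest gap: "These subjects may enroll in this study within 12 months of their withdrawal/completion from the antecedent study".

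SAP 5.4 has a single rule for all subjects, the latest predose value from a list of four sources. The first two are the 003 Week 12/EOT visit and an unscheduled 003 visit in the Week 12 window. The list then ends "visit within 2 weeks of last double-blind dose, or Study ACP-2566-004 Baseline Visit) will be carried over as Baseline information in the present study". So three of the four sources lie in study 003. The second paragraph of 5.4 mentions subjects with a gap, but only to say that their blood is drawn 3 to 14 days before the Baseline visit. It does not state the protocol's exception.

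SAP 19 says: "No changes are made to the analyses specified in the protocol".

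**The concern.** For subjects kept out by COVID-19, the protocol excludes a source of Baseline data that the SAP's rule still admits, and the SAP does not declare the difference. If the rule falls back on a 003 value, the main change-from-Baseline result for that subject and measure covers the time off study as well as the weeks on open-label trofinetide. It is still labelled as change over the treatment weeks alone. A programmer working from SAP 5.4 would produce this result with no signal that anything was wrong.

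**Working it through.** The plan states no figure to reproduce, because the study is descriptive and not powered. The check sets the two rules side by side, then asks where they can differ and by how much.

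**1. The two rules for a subject with a gap.** The SAP rule is read as the latest non-missing predose value in its list. The protocol rule is the same with 003 values excluded. Both were applied with gaps of 30, 180 and 365 days, and the result was the same for each gap:

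| 004 Baseline value | SAP 5.4 selects | Protocol 9.5.1 gives |
|---|---|---|
| Present | 004 value | 004 value |
| Missing | 003 value | No Baseline |

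The rules differ only in the second row.

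**2. When the 004 value can be missing.** Most measures are repeated for these subjects. Protocol 3.1.1 requires all efficacy scales except the CGI-I before the first dose, protocol 6.2.4 a new triplicate ECG, and protocol 6.2.5 a new blood draw. Three routes remain:

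- RTT-COMC at an off-site Baseline visit. Protocol 6.1.7 says "the RTT-COMC should be completed if possible, but it is not required".
- Urinalysis. Protocol 6.2.5 allows for failure: "When collection of a urine sample proves impractical or impossible". Under SAP 14.2 this reaches the shift tables and the numeric changes. The urinalysis criteria in SAP Table 6 do not use Baseline.
- ICND total. SAP 5.2.11 makes it missing if any one of the four health-problem scores is missing. The route matters only if the total could be scored in 003 and again at Visit 5, but not at the 004 Baseline.

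**3. How long the stated change could really be.** Input: a gap of up to 12 months (protocol 4.1), about 52 weeks. True span = 52 + nominal week. Off-study share = 52 / true span.

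| Nominal week | Longest true span | Off-study share | Measures |
|---|---|---|---|
| 2 | 52 + 2 = 54 weeks | 52/54 = 96% | RTT-COMC, urinalysis |
| 12 | 52 + 12 = 64 weeks | 52/64 = 81% | RTT-COMC, urinalysis |
| 26 | 52 + 26 = 78 weeks | 52/78 = 67% | RTT-COMC, urinalysis |
| 40 | 52 + 40 = 92 weeks | 52/92 = 57% | RTT-COMC, urinalysis, ICND total |

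The ICND is scheduled only at Baseline and Visit 5 (protocol 6.1.4), so the earlier rows do not apply to it for a subject who stays on study. These are upper limits for one subject at the longest gap.

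**4. How many subjects.** The documents give neither the share of subjects with a gap (f) nor the share of those with no 004 value for a given measure (m). With N = 180 (protocol 9.3), the number affected is 180 × f × m. Assuming f from 5% to 20% and m from 2% to 25%:

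- lowest: 180 × 0.05 × 0.02 = 0.18
- middle: 180 × 0.10 × 0.10 = 1.8
- highest: 180 × 0.20 × 0.25 = 9

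The resulting shift in a mean cannot be computed. It depends on the difference between the 003 value and a 004 value that is missing by definition.

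**The case against.** The best defence is that the documents nearly close the gap themselves. The latest-value rule selects the 004 value whenever there is one, and these subjects have their scales, ECG and bloods repeated. SAP 1 says that the plan is to be read together with the protocol. SAP 5.4 is also qualified by a remark on applicability, and it closely follows the protocol synopsis, which states the carry-over without the exception. The first of these points stands and keeps the effect small. The others do not restore the exception. The remark on applicability has the CGI-I as its only example, and protocol 9.5.1 is the more specific text.

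It is also fair to say that protocol 9.5.1 names only Week 12/EOT data. Excluding the other two 003 sources goes beyond its words. It follows the intent, because those values are about as old.

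A reader might infer more than the documents support:

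- *That subjects with a gap are generally measured from 003.* They are not. This happens only where the 004 value is missing.
- *That their laboratory Baseline defaults to 003, because the 3-to-14-day draw is not in the source list.* The next paragraph of SAP 5.4 gives Baseline values as the purpose of that draw. The omission should be repaired, but the intent is clear.
- *That the open lower limit of the Baseline window in SAP Table 2 is a fault of its own.* Section 5.4, not the window, decides which visits qualify, and an open limit is needed to admit the earlier blood draw.
- *That the ECG passages contradict each other.* Footnote c of the schedule (protocol Table S-2, SAP 21.1) gives the 003 ECG as the predose Baseline for 003 completers. Protocol 6.2.4 contains the same sentence and follows it with the COVID-19 exception. The footnote is a shortened form, and the latest-value rule selects the 004 ECG anyway.
- *That the fallback is biased by loss of effect off drug.* Protocol 1.3 reports such loss in Phase 2 and illustrates it with the RSBQ. It shows nothing for RTT-COMC, urinalysis or the ICND.

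**Conclusion.** The point holds, with a small effect. For subjects under the exception in protocol 9.5.1, SAP 5.4 states a rule that can select a value the protocol excludes, so SAP 19 is inaccurate on this point. This is a wrong rule rather than a missing detail, but it operates only when the 004 Baseline value is absent. For an affected subject and measure, the stated change could include up to about 52 weeks off study. The number affected is unknown and probably small: between about 0 and 9 of 180 per measure under the assumed ranges. No hypothesis test is planned, so no error rate is involved. The conclusion rests on reading the latest value as the latest non-missing one, and on applying the exclusion to all three 003 sources by intent.

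**What to change.** In SAP 5.4, add that for subjects covered by the COVID-19 exception in protocol 9.5.1, only values from the 004 Baseline visit or the blood draw 3 to 14 days before it count as Baseline. If neither exists, Baseline is missing. Name that draw in the source list, and keep the current rule for all other subjects. With this change, SAP 19 becomes correct on this point.

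Two editorial corrections can be made at the same time. SAP 5.1 should cite Section 5.4, not 5.5, for the baseline definition. ECG footnote c in both schedules should be aligned with the full text of protocol 6.2.4.

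The cost is mainly SAP wording, plus the same footnote in the protocol schedule. A few subjects would lose a change score, or their place in a shift-table denominator, for a parameter with no valid 004 Baseline. For Week 12/EOT data, protocol 9.5.1 already implies that loss.
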